1. RESEARCH GOALS

This study will investigate whether initial treatment with high-dose intravenous immunoglobulin plus prednisolone (PSL) yields better results than standard treatment (high-dose intravenous immunoglobulin) in patients with Kawasaki disease (KD). The primary endpoint of this study is incidence of coronary artery abnormalities (CAA) during the study period. The secondary endpoints include incidence of CAA at 4 weeks after enrollment, Z scores for the right coronary artery and left main coronary trunk and anterior descending artery, days of fever after enrollment, incidence of need for additional rescue therapy, serum levels of C-reactive protein (CRP) at Weeks 1 and 2 after enrollment, and incidence of severe adverse events.

2. BACKGROUND AND RATIONALE FOR THE STUDY

2.1. Subjects

2.1.1. Disease studied and current standard treatment

[figure not shown]
KD is a vasculitis syndrome of unknown cause, first reported by Tomisaku Kawasaki in 1967.¹⁾ It is the leading cause of acquired heart disease in developed countries.²⁾ Because the causes of KD have not been identified, there are no specific therapies for KD patients. Furusho et al³⁾ in 1984 and Newburger et al⁴⁾ in 1986 reported that treatment with intravenous immunoglobulin (400 mg/kg×4 or 5 days) plus aspirin reduced the incidence of CAA as compared with aspirin alone (Furusho: 19/45 [42%] vs. 6/40 [15%]; Newburger: 14/79 [18%] vs. 3/79 [4%]).

[figure not shown]
In 1991, Newburger et al⁵⁾ reported the efficacy of high-dose intravenous immunoglobulin (2 g/kg×single day) plus aspirin therapy: the relative risk of CAA formation was 1.94 (95%CI 1.01-3.71) at Week 2 and 1.84 (95%CI 0.89-3.82) at Week 7. Since then, high-dose intravenous immunoglobulin plus aspirin therapy (IVIG) has become the standard therapy for acute KD.⁶⁾ IVIG is clearly effective and has adequate safety. However, approximately 20% of KD patients did not become afebrile despite IVIG administration⁷⁾⁻⁹⁾; those IVIG nonresponders are considered to be at high risk for CAA. These facts suggest the importance of establishing a new therapeutic strategy for severe KD patients, particularly IVIG nonresponders.

2.1.2. Reasons for selection of subject groups

IVIG is an excellent therapy in resolving inflammation from KD and reducing the occurrence of CAA. However, approximately 20% of KD patients have persistent or recurrent fever after IVIG; further, many studies have shown that these patients are at increased risk of developing CAA. Early identification of likely IVIG nonresponders who will require additional therapy

might reduce the risk of coronary artery injury. For this purpose, Kobayashi et al¹⁰⁾ developed a risk score to predict IVIG nonresponse among KD patients before the initiation of IVIG.

Using this risk score, KD patients can be stratified as being at high (5 points or more) or low risk (4 points or less) for IVIG nonresponse; IVIG nonresponders were identified with a sensitivity of 74% and a specificity of 80%, and CAA was identified with a sensitivity of 77% and a specificity of 71%. The risk score thus might enable us to identify KD patients who require more intensive initial therapy. High-risk patients can then be started on more intensive initial treatments. Moreover, identification of patients for whom standard IVIG will likely suffice allows such patients to be spared unnecessary treatment.

2.2. Rationale for establishing treatment regimen

Corticosteroids are administrated for various forms of vasculitis because of their strong anti-inflammatory effects. However, many physicians have hesitated to use corticosteroids in KD because an early report¹¹⁾ showed a high incidence of CAA in a group that received a prolonged course of oral PSL alone. However, subsequent retrospective studies¹²⁾⁻¹⁶⁾ of the effects of corticosteroids in KD have shown either no adverse effects or possible benefits. Wooditch and Aronoff¹⁷⁾ concluded in a meta-analysis that inclusion of corticosteroids in aspirin-containing regimens for initial therapy of KD reduced the incidence of CAA.

In 2006, Inoue et al¹⁸⁾ reported in a randomized, open-label, unblinded trial that IVIG plus PSL therapy decreased the incidence of CAA and treatment nonresponse, although potential methodological flaws were noted in the study.¹⁹⁾ In 2007, Newburger et al²⁰⁾ conducted a randomized, double-blinded, placebo-controlled trial of the efficacy of adding a single dose of pulsed intravenous methylprednisolone to conventional IVIG therapy. Although pulsed corticosteroid therapy with IVIG did not improve coronary artery outcomes, post-hoc subgroup analysis suggested that initial therapy with intravenous methylprednisolone plus IVIG might provide a benefit for children at highest risk for resistance to initial IVIG.

The principal difference between the 2 studies was the duration of corticosteroid administration.

Although the total dose of corticosteroids was similar, the median duration of PSL administration was 21 days in the earlier study, as compared with 1 course of 30 mg/kg methylprednisolone in the US study. The serum half-life of a pulsed dose of methylprednisolone is approximately 3 hours²¹⁾, and PSL was administered for 3 weeks in the Japanese study. Although KD is self-limiting, fever persists approximately 2-3 weeks if untreated.¹⁾ Duration of corticosteroid administration might be more important than maximum concentration of corticosteroid in suppressing inflammation and vasculitis in KD. Thus, the RAISE Study group selected conventional PSL therapy combined with IVIG plus aspirin, as reported by Inoue et al.

2.3. Study Design

2.3.1. Planned Phase III study design

Interventional, Prospective, Randomized, Open-label, Blinded-Endpoint (PROBE) study

2.3.2. Endpoints

Primary

• Incidence of CAA during the study period

Secondary

- Incidence of CAA at Week 4 after enrollment
- Z scores²²⁾ for right coronary artery and left main coronary trunk and anterior descending artery
- Incidence of need for additional rescue therapy
- Days of fever after enrollment
- Serum levels of CRP at Weeks 1 and 2 after enrollment
- Incidence of severe adverse events

2.3.3. Clinical hypotheses and reason for number of registrants

The principal hypothesis of the present study is that patients with severe KD who receive the study treatment (IVIG with PSL) will have a significantly lower incidence of CAA during the study period as compared with the group receiving standard treatment (IVIG). If this does indeed prove to be true, then initial treatment with IVIG plus PSL will be judged to be more effective.

The target enrollment was set using data obtained from 1123 consecutive KD patients from August 2000 to August 2007 at 13 hospitals in Gunma and Saitama prefectures, Japan. ²³⁾ Eight KD patients who presented with CAA at admission and 109 KD patients with missing values were excluded from this study. Thus, data from 1006 KD patients (IVIG group n=896, IVIG+PSL group n=110) were analyzed. Of the 110 patients in the IVIG+PSL group, 90 were participants of a previously reported randomized trial. ¹⁸⁾ The other 20 patients were given IVIG+PSL according to the attending doctor's recommendations, except for 1 patient

whose parents desired treatment with IVIG+PSL. The table below shows clinical and coronary outcomes in the high-risk group.

	IVIG (n=298)	IVIG+PSL (n=48)
Nonresponse to treatment	51.7	20.8
Incidence of coronary artery abnormality during 1 month	18.1	6.3
Incidence of coronary artery abnormality at 1 month	8.4	4.2

The primary endpoint of the RAISE Study is to assess whether the incidence of CAA in the study treatment is significantly lower than that of the standard treatment during the study period. Based on the above data, the required sample size was calculated with the assumption that IVIG plus PSL would reduce the fraction of patients with CAA during the study period from 18% to 8%. With a 2-sided test, an α level of 0.05, and a power of 80% and assuming that 10% of the patients would not complete the study, a total sample of 392 patients would be required. Analyses were intent-to-treat. Fisher's exact test was used to test the null hypothesis, i.e. that the incidence of CAA would be equal between the 2 treatment groups during the study period.

3. DEFINITIONS USED IN THE STUDY

3.1. Diagnosis of KD

A diagnosis of KD is based on the presence of fever accompanied by at least 4 of the following symptoms: bilateral conjunctival injection, changes in the lips and oral cavity, nonpurulent cervical lymphadenopathy, polymorphous exanthema, and changes in the extremities. Patients with incomplete KD (fever with 3 or fewer of the above symptoms) at diagnosis will be enrolled if they receive a diagnosis of KD from the attending physician. These diagnostic criteria comply with the Diagnostic Guidelines for Kawasaki Disease (Fifth Revised Edition).²⁴⁾

3.2. Using risk score to identify severe KD patients

Disease severity will be assessed using the risk score developed by Kobayashi et al.¹⁰⁾ This risk scoring system was based on a multiple logistic regression analysis of 750 consecutive KD patients given IVIG. Seven variables were included in the risk score. Points are assigned using the threshold values shown below (higher scores indicate greater disease severity).

Variable	Threshold value	Points
Sodium	≤133 mmol/L	2
AST	≥100 IU/L	2
Illness days at diagnosis	≤ 4 illness days	2
%neutrophils	≥80%	2
CRP	≥10 mg/dL	1
Age in months	≤12 months	1
Platelet count	≤300,000/mm ³	1

[figure not shown]
The total number of points assigned to a patient is that patient's risk score. If a laboratory test was performed twice or more before initial therapy, the highest value was chosen for AST, % neutrophils, and CRP, while the lowest value was chosen for sodium and platelet count. In the present study, patients will be defined as high risk if they have a total score of 5 points or higher, and only these high-risk patients will be randomly assigned to the 2 treatment groups.

[figure not shown]
3.3. Definition of fever

Febrile: ≥37.5°C

Afebrile: <37.5°C for ≥24 hours.

Absence of fever is defined as a body temperature lower than 37.5°C for at least 24 hours, using an electronic thermometer in the axilla. In calculating time to resolution of fever, start of treatment is defined as Hour 0. Fever resolution within 24 hours is defined as "on the first day," within 48 hours as "on the second day," etc., with subsequent 24-hour periods each counted as a "day."

[figure not shown]

[figure not shown]
3.4. Definition of treatment nonresponse

Treatment nonresponse is defined as no response to initial treatment, or a relapse.

1. Nonresponse to initial treatment: fever does not resolve within 24 hours after completion of initial IVIG administration.

2. Relapse: fever initially resolves, but then returns, and is accompanied by other symptoms of KD, in the absence of other causes of fever (eg, bacterial or viral infections)

3.5. Definition of coronary artery abnormalities

The coronary artery will be assessed using 2-dimensional echocardiography obtained at baseline, week 1 (6-8 days after enrollment), week 2 (12-16 days after enrollment), and week 4 (24-32 days after enrollment). The coronary artery must be measured at segments 1, 5, and 6. Segments 2, 3, 7, and 11 will also be measured, if possible. Cardiac function and presence of cardiac effusion (more than 1 mm: posterior wall of left ventricle during systole) should also be assessed. All echocardiographic examinations will be recorded from start to finish using a digital video recorder provided by the RAISE Study Office. All examinations will be recorded on DVD and sent to the RAISE Study Data Coordination Center. Using video of digitally recorded 2-dimensional echocardiograms at facilities, all echocardiograms will be interpreted at a core laboratory by 2 pediatric cardiologists blinded to patient identity and illness day. If these cardiologists disagree, a third pediatric cardiologist will make the final decision regarding the presence of abnormalities.

A coronary artery will be defined as abnormal when the luminal diameter is ≥ 3.0 or ≥ 4.0 mm in a child aged < 5 or ≥ 5 years, respectively, when the internal diameter of a segment is ≥ 1.5 times that of an adjacent segment, or when the luminal contour is clearly irregular.²⁵⁾

4. PATIENT SELECTION CRITERIA AND TREATMENT ASSIGNMENT

Eligible patients must fulfill the following inclusion criteria.

4.1. Inclusion criteria

- 1. Severe KD with a risk score of 5 points or higher
- 2. Receipt of written informed consent from parents or legal guardians, as per the guidelines of the local institutional review boards that approved the study protocol.
- 3. Exclusion of other conditions that mimic KD, eg, scarlet fever, Epstein-Barr infection, adenovirus infection, Yersinia infection, measles, and Stevens-Johnson syndrome.

4.2. Exclusion criteria

The following patients will be excluded.

- 1. Patients who do not provide informed consent for study enrollment
- 2. Patients with a previous history of KD
- 3. Patients who present 9 days or later after disease onset (onset defined as first day of fever)
- 4. Patients with CAA before study enrollment
- 5. Patients with fever resolution before study enrollment
- 6. Patients who received corticosteroid in the previous 28 days, either orally, intravenously,

or by intramuscular or subcutaneous injection

- 7. Patients who received IVIG in the previous 180 days
- 8. Patients with any of the following severe diseases: immunodeficiency, chromosomal anomalies, congenital heart diseases, metabolic diseases, nephritis, collagen diseases.
- 9. Patients with suspected infectious disease, including sepsis, septic meningitis, peritonitis, bacterial pneumonia, varicella, influenza, and others.

[figure not shown]
5. TREATMENT PLAN

5.1. Treatment protocol

5.1.1. Initial treatment

[figure not shown]
(IVIG Group: treated with IVIG)

Patients will be treated with intravenous immunoglobulin 2 g/kg given over 24 hours. Aspirin will also be given at a dose of 30 mg/kg/day until the patient is afebrile, followed by aspirin 3–5 mg/kg/day until 28 days after enrollment. Aspirin should be continued until 2 months after enrollment

(IVIG+PSL Group: treated with IVIG plus PSL)

Patients in the IVIG+PSL group will also receive the same IVIG with aspirin regimen plus prednisolone sodium succinate (2 mg/kg/day, in 3 divided doses) given by intravenous injection for 5 days. After fever resolves, PSL will be given orally. When CRP level normalizes (≤0.5 mg/dL), the PSL dose will be tapered over 15 days in 5-day steps from 2 to 1 to 0.5 mg/kg/day. Famotidine will be administered with PSL. The maximum dose of PSL is 60 mg/day; thus, patients weighing more than 30 kg will be tapered from PSL 60 to 30 to 15 mg/day.

5.1.2. Prohibited medications

Use of nonsteroidal anti-inflammatory drugs (NSAIDs; e.g. acetaminophen, mefenamic acid) except aspirin and flurbiprofen is not allowed, because a secondary endpoint of the study is days of fever after enrollment, and the use of NSAIDs could influence the results.

5.2. Concomitant therapy

Attending doctors should provide additional rescue therapy for nonresponders, using the recommendations of the "Guidelines for Acute Phase Therapy for Kawasaki Disease", promulgated by the Japanese Society of Pediatric Cardiology and Cardiac Surgery in 2003.²⁶⁾ The following is a general outline of these supplementary treatment modalities.

5.2.1. Treatment options for treatment nonresponse

Although additional rescue therapy for IVIG nonresponders has been examined, the evidence is insufficient due to the lack of a controlled study. In Japan, retreatment with IVIG is the most common rescue therapy. The RAISE Study group allows additional rescue therapy and leaves the choice of such therapy to the attending doctor.

(1) Retreatment with IVIG 2 g/kg or 1 g/kg.

At present, the most common treatment option for nonresponders is retreatment with IVIG. Clinical experience suggests that this is the safest supplementary treatment. The American Heart Association Guidelines recommend a single dose of 2 g/kg IVIG, but no controlled trials have confirmed the efficacy of retreatment with IVIG (Evidence level C).⁶⁾

(2) Corticosteroid (pulsed methylprednisolone and/or PSL)

Corticosteroids are widely used for various forms of vasculitis. However, the use of corticosteroids for KD patients has been limited because of an early report showing a high incidence of CAA in a group that received a prolonged course of oral PSL alone. However, recent reports indicate that treatment with oral or intravenous PSL, or pulsed methylprednisolone, might indeed be effective ether as an initial treatment for all patients or in patients who fail to respond to initial IVIG. Some studies have reported that corticosteroid treatment might lead to quicker suppression of serum inflammatory cytokines. 27,28)

(3)Ulinastatin

In Japan, several centers have reported the efficacy of ulinastatin. However, this is an offlabel use for the drug, and optimal doses and administration durations are not established. In addition, adverse effects such as rashes and neutropenia have been reported. Ulinastatin should not be simultaneously administered with IVIG via the same route.

- (4)Increased dose of aspirin
- (5)Nonsteroidal immunosuppressants (eg, cyclosporin A, methotrexate)

 Patients unresponsive to IVIG and standard supplementary therapies have been treated

with a variety of immunosuppressants, and occasional case reports have reported successful outcomes. $^{29),30)}$

(6) Anti-TNF α antibodies (e.g. infliximab)

Anti-TNF- α antibodies suppress production of various inflammatory cytokines by specifically blocking TNF α activity. Recently, this treatment was reported to be effective for severe KD patients. Studies have investigated the use of anti-TNF α antibodies in adults with worsening infectious diseases, such as progressive cardiac insufficiency or recurrent tuberculosis, as well as in infusion events and for treatment of malignant tumors. 34

(7)Plasma exchange

Successful use of plasma exchange has been reported in severe KD patients who do not respond to other treatments.³⁵⁾

Treatment	Drug name	Schedule	Adverse effects and other considerations
Corticosteroids	Prednisolone	Start at 2 mg/kg/day, then tapered (as in present study)	Fever might return when dosage is reduced, infection, hypertension, thrombosis,
	Methylprednisolone	10-30 mg/kg/day in 1-3 doses, IV	electrolyte imbalance
Neutrophil elastase inhibitors	Ulinastatin	5000 units /kg; 3-6 times/day, several days IV	Leukopenia, rash
Nonsteroidal immunosuppressants	Cyclosporin A Methotrexate	1-4 mg/kg/day in 2-3 divided doses 10 mg/body surface area	Infection, cyclosporin encephalopathy, abnormal liver function, mucous membrane disorders
Anti-TNF $lpha$ antibodies	Infliximab	5 mg/kg/day x 1 day, 2-hour IV drip	Shock, worsened cardiac insufficiency, tuberculosis
Plasma exchange (5% albumin solution)		Amount equivalent to circulating blood volume, 1-3 days	Shock, vascular injury

5.3. Withdrawal criteria

- 1. If a patient is identified as ineligible after enrollment, due to misdiagnosis, misclassification of severity, etc.
- 2. If the RAISE study office determines that the patient should be excluded due to an unacceptable violation.
- 3. If the patient or their guarantor requests termination of the protocol treatment.
- 4. If the patient's attending physician determines that treatment should be terminated.
- 5. If a patient dies during the protocol treatment.
- 6. If the Data and Safety Monitoring Board decides to be terminate the study because of adverse events.
- 7. If patient information is no longer obtainable due to the patient having changed hospitals, etc.

6. RANDOMIZATION AND ASSIGNMENT ADJUSTMENT

6.1. Case registration

Randomization and allocation of participants is performed via a web-based central allocation system at the University hospital Medical Information Network (UMIN). Among patients that fulfill the inclusion criteria, the attending doctor will explain the study plan to the patients and/or their parents. If informed consent is obtained, the attending physician will enroll the patient after entering the required items (initials of participant, sex, age in months, days of illness at diagnosis, % neutrophils, platelet count, AST, sodium, CRP, and inclusion and exclusion criteria) via the web-based allocation system on the homepage of the RAISE Study. All case registration and group assignment will be done by accessing the Internet home page for RAISE Study researchers: registration and group assignment will not be done by phone or email, except in emergencies. Patient registration and group assignment will be kept on file on the Internet Medical Research Data Coordinating Center (INDICE) server, and online access to this information is possible only through the RAISE Study researcher home page (for security reasons). To access the RAISE Study researchers' site, a UMIN ID and general password are required. To proceed further, to the patient registration page, a UMIN ID and UMIN INDICE password are required.

6.2. Random assignment and assignment adjustment factors

Dynamic random assignment of patients to their respective groups will be done using the minimization method at a 1:1 ratio. The adjustment factors include sex, age, and institution, classified by method of additional rescue therapy (Group A; IVIG retreatment only, Group B; IVIG retreatment and/or conventional dose of PSL, Group C; IVIG retreatment and/or pulsed dose methylprednisolone with or without subsequent PSL, Group D; IVIG retreatment and/or conventional dose of PSL and/or pulsed dose methylprednisolone with or without subsequent PSL and/or infliximab).

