12. STATISTICS

12.1. Principal analyses and criterion

The main goal of the present study is to determine whether, as compared with standard IVIG treatment, treatment with IVIG plus PSL results in a significant reduction in the primary endpoint, i.e. the incidence of CAA during the study period. To test the null hypothesis (namely, that the incidence of such complications will be the same in both groups), Fisher's exact test will be used to compare all applicable cases in the 2 groups. Because it is possible that the trial treatment could result in worse outcomes than standard treatment, all testing will be 2-sided. The significance level for all tests will be 5% (2-sided).

If statistical analysis reveals that the incidence of CAA during the study period is significantly lower in the trial treatment group than in the standard treatment group, the conclusion will be that the trial treatment with IVIG plus PSL is the more effective treatment. If no such significant decrease is found, the conclusion will be that treatment with IVIG remains the standard treatment for KD.

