12.4.2. Analysis of secondary endpoints related to efficacy

The secondary endpoints related to treatment efficacy include incidence of CAA at week 4 after enrollment, Z scores for the right coronary artery and left main coronary trunk and anterior descending artery, days of fever after enrollment, incidence of need for additional rescue therapy, and serum levels of CRP at Weeks 1 and 2 after enrollment. These secondary endpoints will only be analyzed during the interim analysis and at the end of the study, and only as secondary endpoints; there will be no correction for the multiplicity of tests when these endpoints are analyzed.

It is expected that the incidence of CAA at week 4 after enrollment will be lower in the IVIG plus PSL group than in the IVIG group, as this result is expected to be correlated with the largest diameter attained during the enlargement of the coronary artery, while these treatments are being administered.

As for incidence of need for additional rescue therapy, this can be considered to reflect the effectiveness of the treatments. It is therefore expected that this incidence will be lower in the IVIG plus PSL group than in the IVIG group.

As for days of fever after enrollment and serum levels of CRP at Weeks 1 and 2 after enrollment, these can be considered endpoints that depend on the suppression of KD vasculitis achieved by the treatments. It is therefore expected that, as compared with standard IVIG treatment, the period required for days of fever after enrollment will be shorter, and that serum levels of CRP at Weeks 1 and 2 after enrollment will be lower, in the IVIG plus PSL group.

Fisher's exact test will be used to evaluate the incidence of CAA at Week 4 after enrollment

and the incidence of need for additional rescue therapy; the interval estimation will be done with exact confidence intervals based on the binomial distribution.

Z scores for the right coronary artery and left main coronary trunk and anterior descending artery, days of fever after enrollment, and serum levels of CRP at Weeks 1 and 2 after enrollment will first be tested for normality with the Kolmogorov-Smirnov test. Variables that are found to have a normal distribution will be compared using the unpaired t-test; those with a non-normal distribution will be compared using the Mann-Whitney U-test.

12.5. Termination of the study if the incidence of giant coronary aneurisms in the trial treatment group is high

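### The primary test is an unadjusted Fisher's exact test despite minimised allocation; it falls short of 80% power at the planned evaluable number, mostly because Fisher is conservative

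*Protocol*

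**What the plan says.** Protocol section 6.2 states: "Dynamic random assignment of patients to their respective groups will be done using the minimization method at a 1:1 ratio". It continues: "The adjustment factors include sex, age, and institution, classified by method of additional rescue therapy", and lists four classes, A to D, according to the rescue treatments an institution uses. The third factor is therefore a property of the site, known before randomisation. It is not the rescue therapy that an individual patient later receives. No age categories are given.

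The primary comparison uses none of these factors. Section 12.1: "Fisher's exact test will be used to compare all applicable cases in the 2 groups". Section 2.3.3 says the same ("Fisher's exact test was used to test the null hypothesis"), with analysis by intention to treat. Section 12.3.2 applies Fisher's test again at the interim look, with a stopping threshold of p < 0.0034.

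Sections 2.3.3 and 12.2 plan for 18% versus 8%, two-sided alpha 0.05 and 80% power. That gives 176 evaluable patients per group (352), and 196 per group (392) after allowing for 10% drop-out.

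**The concern.** Minimisation makes the groups more alike on the chosen factors than simple randomisation would. If a factor predicts coronary artery abnormalities (CAA), a test that ignores it counts that balanced variation as noise and loses some power. The protocol gives grounds to think age and institution class may matter:

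- Age of 12 months or less scores a point in the risk score (3.2), and that score has some ability to identify CAA (2.1.2).
- The diameter cut-off for an abnormal artery changes at age 5 (3.5).
- In the planning data 51.7% of high-risk patients on IVIG alone did not respond (2.3.3), so the rescue practice of the site could affect many control patients.

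A second source of loss is separate from adjustment. Fisher's exact test is conservative, and the sample size appears to have been computed for a different test. The question is how much power is lost and how much belongs to each source.

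**Working it through.** **1. Reproduce the planned number.** Inputs from 2.3.3 and 12.2: p1 = 0.18, p2 = 0.08, mean 0.13, two-sided alpha 0.05, power 80%. The usual pooled normal formula without continuity correction is

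n = [1.960·√(2·0.13·0.87) + 0.842·√(0.18·0.82 + 0.08·0.92)]² / 0.10²
= [1.960·0.4756 + 0.842·0.4703]² / 0.01 ≈ 176.4.

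Rounded up this is 177; the protocol has 176. Unpooled and arcsine versions give 174 and 172. The continuity-corrected version, which is closer to Fisher's test, gives 196. Drop-out: 176/0.9 = 195.6, so 196 per group, as stated. The 176 is therefore an uncorrected chi-square-type number.

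**2. Exact power and size of the test that is named.** These come from summing binomial probabilities over all tables that each test rejects at 0.05. Size is at a common rate of 13%.

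| Per group | Fisher power | Uncorrected chi-square power | Fisher size | Chi-square size |
|---|---|---|---|---|
| 176 | 76.5% | 81.0% | 0.035 | 0.050 |
| 196 | 81.1% | 84.7% | 0.035 | 0.049 |

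Fisher's conservatism costs 81.0 − 76.5 = 4.5 points at 176 per group and 84.7 − 81.1 = 3.6 points at 196. In steps of 4, Fisher first reaches 80% at about 192 per group.

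**3. What adjustment adds.** The protocol does not say how strongly the factors predict CAA, so a range was assumed: none; weak (odds ratio 1.5 for sex and for age); moderate (2 and 2, class up to 2); strong (3 and 3, class up to 3). The simulation also assumed a 60/40 sex split, a 30/70 age split, four equal institution classes and a biased-coin probability of 0.8. It used 352 patients and 2,500 runs per cell, so Monte Carlo error is about 0.8 points. Power:

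| Assumed strength | Fisher | Chi-square | Adjusted logistic (likelihood ratio) | Logistic minus chi-square |
|---|---|---|---|---|
| None | 76.4% | 80.3% | 80.9% | 0.6 |
| Weak | 77.4% | 80.8% | 81.7% | 0.9 |
| Moderate | 79.1% | 82.4% | 83.9% | 1.5 |
| Strong | 76.8% | 79.9% | 83.0% | 3.1 |

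Adjusted logistic regression gains 4.4 to 6.2 points over Fisher. Of that, 3.1 to 3.9 points come simply from leaving Fisher for an unadjusted chi-square. A Cochran-Mantel-Haenszel test over all 16 cells differs from the chi-square by only −1.7 to +1.6 points, because the strata are thin. With all 392 patients, adjusted logistic gains 3.4 to 5.0 points over Fisher.

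**4. Size under minimisation.** Simulated size was 0.028 to 0.044 for Fisher and 0.049 to 0.062 for the likelihood-ratio logistic test. A separate run of 6,000 null trials gave 5.6% for the likelihood-ratio version and 5.1% for the Wald version. Part of the apparent power gain of the likelihood-ratio version is therefore looser size.

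**5. Events available to a model.** Final: 176·0.18 + 176·0.08 ≈ 46. Interim at 200 patients: 200·0.13 = 26.

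The power figures are for a single look at 0.05 and leave the interim look out.

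**The case against.** A reader might infer that the unadjusted analysis is what costs the trial its power, or that it makes the p value invalid. The figures support neither. An unadjusted chi-square recovers most of the loss, and the remaining mismatch with minimisation errs towards caution.

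The case for leaving the plan alone has four parts.

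- Fisher is simple, prespecified and keeps its size below 5%, which suits the aim in 12.3.2 of holding overall alpha below 5%. This stands: a model-based test gives up that guarantee.
- The prognostic strengths are assumed. This also stands, and is why the adjustment component is given as a range that starts near zero.
- Section 2.3.3 calls for intention to treat, and with all 392 patients analysed Fisher has 81.1% power. This is correct, but the plan itself allows for 10% not completing and counts on 352.
- Changing only the final test would put two different tests inside one alpha-spending scheme. This is right, so the change must cover both looks.

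The point is not one that a separate statistical analysis plan would settle, since the protocol itself names the primary test. Such a plan could still add an adjusted sensitivity analysis.

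**Conclusion.** The point holds as a matter of efficiency and of consistency between design and analysis. At 18% versus 8% with 176 evaluable per group, the named test has 76.5% power, 3.5 points below plan. Most of what could be recovered, about 3 to 5 points, is due to Fisher's conservatism and would be lost even if sex, age and institution class had no bearing on CAA. Leaving the factors out costs roughly 0 to 3 points more, and the upper end needs strong effects that the protocol does not document. The exact Fisher figures rest only on the planning rates and group sizes; the adjustment figures also rest on the assumed odds ratios, factor frequencies and biased-coin probability. A positive result under the present plan would not be made doubtful by this.

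**What to change.** In 12.1, make the primary test a prespecified logistic regression of CAA on treatment, sex, age and institution class A to D. State:

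- that class is the site's classification at randomisation, not the patient's own rescue therapy;
- one age coding, most naturally the one used in the minimisation;
- one rule for sparse classes, for example Firth penalisation;
- which test statistic gives the p value, since the likelihood-ratio version ran slightly above 5%.

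Report the adjusted odds ratio and the standardised risk difference with 95% confidence intervals, and keep Fisher's test as a sensitivity analysis. Make the same change in 2.3.3 and in the stopping rule of 12.3.2, so that both looks use one test within the alpha-spending scheme.

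The cost is wording and some checking. No new patients or data are needed: sex and age are entered at registration (6.1) and class is known for each site. The downside is a test whose size is close to 5% (about 4 to 6% in simulation) in place of one that stays below it. Before adoption, the model's size should be checked at the 0.0034 threshold with about 26 events. If the exact guarantee is preferred, the alternative is to keep Fisher and size the trial for it: about 192 evaluable per group instead of 176.
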